Official Title: "Vestibular Rehabilitation and Otolith Dysfunction"

NCT Number: 02652442

Document date: 9-28-2021

Scientific Background: Vestibular Rehabilitation (VR) is the treatment of choice for patients experiencing dizziness, imbalance, and mobility impairments related to vestibular dysfunction. VR typically includes gaze stability exercises, which were developed to facilitate vestibular compensation of the semicircular canal-mediated vestibulo-ocular reflex (VOR). A critical signal to induce adaptation is retinal slip during head movements; thus, adaptation exercises involve head rotation while focusing on a target. Most studies examining the effectiveness of VR have used only tests of VOR function (caloric and rotational tests) that measure horizontal semicircular canal to determine vestibular loss. Thus, little is known about interventions to facilitate vestibular compensation of the otolith organs.

The concept of using centrifugation for otolith adaptation may be similar to using gaze stability exercises for VOR adaptation. Recent studies have demonstrated adaptation following otolith organ stimulation using centrifugation (or linear acceleration), but there is no data regarding optimum stimulus parameters. The purpose of this study is to determine optimal off-axis distance of the rotary chair, duration of off-axis rotation (OAR), and training schedule for otolith adaptation.

Study Objectives: The goal for testing different training protocols in healthy controls is: 1) to determine optimal stimulus parameters (off-axis distance of the rotary chair, duration of off-axis rotation, and training schedule) that will be used to treat patients with otolith dysfunction and 2) to demonstrate otolith plasticity with a given set of stimulus parameters.

Study design: Sequential assignment to stimulus parameters (off-axis distance, duration of off-axis rotation, training schedule)

Study Protocol: For healthy controls, only unilateral centrifugation (UC) training (randomized for right or left ear off-axis) will be performed. Direction (CW or CCW) of off-axis rotation (OAR) will be standardized so that subjects are facing forward in the direction of rotation.

Primary outcome measure: Static subjective visual vertical (SVV) assesses spatial perception and is influenced by otolith function. Perception of vertical is measured in a darkened room with subject seated upright. The test assesses an individual's ability to adjust a laser line to be parallel with true vertical in the absence of any other visual cues. The start position of line for SVV testing is randomized and participants are instructed to use the track ball to position the line in a vertical position. Five trials are completed, and the software calculates the distance (in degrees) from vertical. The average of the trials is calculated and used for data analysis.

Experiment 1. Determination of optimal distance of OAR (n = 5 subjects). Each subject will complete training at chair position (A) followed by (B) with at least 2 weeks in between each training session until static SVV returns to normal.

Training schedule	Chair position off-axis (cm)	Chair acceleration/ deceleration ($^{\circ}/s^2$)	Chair velocity ($^{\circ}/s^2$)	Duration of UC	Cycles per session	Measures
5 consecutive sessions (M-F)	(A) 3.5	5	300	90 sec accelerate to/ maintain constant velocity on-axis rotation; 1 min OAR at constant velocity; 60 sec to decelerate	5	Static SVV (5 trials) at start/end of each session
same	(B) 7.0	same	same	same	same	same

Experiment 2. Determination of duration of OAR (n = 5 subjects). Each subject will complete training at optimal chair position (determined in Exp. 1) for duration (A) followed by (B) with at least 2 weeks between each training session.

Training schedule	Chair position off-axis (cm)	Chair acceleration/ deceleration ($^{\circ}/s^2$)	Chair velocity ($^{\circ}/s^2$)	Duration of UC (sec)	Cycles per session	Measures
5 consecutive sessions (M-F)	Optimal distance as determined in Exp. 1	5	300	(A) 90 sec accelerate to/ maintain constant velocity on-axis rotation; 1 min OAR at constant velocity; 60 sec to decelerate	5	Static SVV (5 trials) at start/end of each session
same	same	same	same	(B) 90 sec accelerate to/ maintain constant velocity on-axis rotation; 3 min OAR at constant velocity; 60 sec to decelerate	same	same

Experiment 3. Determination of optimal training schedule (n = 5 subjects). Each subject will complete training at optimal chair position (determined in Exp. 1) for optimal duration (determined in Exp. 2) with intermittent schedule (B) at least 2 weeks after completion of Experiment 2.

Training schedule	Chair position off-axis (cm)	Chair acceleration/ deceleration ($^{\circ}/s^2$)	Chair velocity ($^{\circ}/s^2$)	Duration of UC (sec)	Cycles per session	Measures
(A) 5 consecutive sessions (M-F)	Optimal distance as	5	300	90 sec accelerate to/ maintain constant velocity on-axis rotation; optimal	5	Static SVV (5 trials) at start/end of each session

	determined in Exp. 1			duration of (determined in Exp. 2) OAR at constant velocity; 60 sec to decelerate		
(B) 2x/week x 3 weeks until 5 sessions completed	same	same	same	same	same	same

Statistical Analysis Plan: All data will be summarized using descriptive statistics. To examine the extent to which centrifugation parameters (distance, duration, schedule) impact the primary outcome (Subjective Visual Vertical, SVV) for healthy controls, paired t-tests will be used to examine change in static SVV (pre- to post-centrifugation). Alpha level is 0.05. No adjustments will be made for multiple comparisons.

Office for the Protection of Human Research Subjects • [name]

[contact] [contact]

IRB APPROVAL – Initial Expedited Review

December 4, 2015

To : VA R&D

RE: [name]

Re: Vestibular Rehabilitation and Otolith Dysfunction

IRB#: 1215.2 S

ORSPA #:

The following items were reviewed and approved by an expedited process:

- New protocol submission, project summary, Otolith Rehab grant, dgi-fga data collection sheet, Locus of Control Scale survey, Disability Rating Scale survey, mmse survey, Health questionnaire Otolith Rehab, Vestibular Activities and Participation Measure survey, VAS scales, PASE, Geriatric Depression Scale, Geriatric Anxiety Inventory, ABC scale survey, ICD version 11/17/2015, CV for PI, HIPAA waiver

On December 3, 2015, a final approval was granted for a period not to exceed 12 months and will expire on December 2, 2016. The expedited approval of the study will be reported to the convened board on the next agenda.

The following **enclosed stamped, approved Informed Consent Documents** have been stamped with the approval and expiration date and these documents must be copied and provided to each participant prior to participant enrollment:

- Informed Consent Document (ICD 11.17.2015 stamped 12.03.2015)

Federal regulations require that a copy is given to the subject at the time of consent.

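### SVV is scored as distance from vertical with no sign and no alignment to the trained ear, although the ear is randomised; if the after-effect is lateralised, the pooled paired t-test understates or misses it

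*Combined protocol and SAP*

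**What the plan says.** **Allocation (Study Protocol).** For healthy controls, "only unilateral centrifugation (UC) training (randomized for right or left ear off-axis) will be performed". The rotation sense follows from the ear: "Direction (CW or CCW) of off-axis rotation (OAR) will be standardized so that subjects are facing forward in the direction of rotation". Right- and left-ear subjects therefore receive mirror-image set-ups.

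**Outcome (Primary outcome measure).** The test is described as the "ability to adjust a laser line to be parallel with true vertical in the absence of any other visual cues". Five trials are taken, and "the software calculates the distance (in degrees) from vertical. The average of the trials is calculated and used for data analysis". Whether the distance carries a sign is not stated, and it is not referred to the trained ear.

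**Timing (Experiment 1).** The measure is "Static SVV (5 trials) at start/end of each session". The two chair positions are separated "with at least 2 weeks in between each training session until static SVV returns to normal".

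**Analysis (Statistical Analysis Plan).** The plan is that "paired t-tests will be used to examine change in static SVV (pre- to post-centrifugation". Alpha is 0.05. There is no ear term, stratification or recoding.

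**Aim (Study Objectives).** The second objective is "to demonstrate otolith plasticity with a given set of stimulus parameters".

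**The concern.** A one-sided stimulus applied to a randomly chosen side invites the expectation that perceived vertical tilts one way after right-ear training and the other way after left-ear training. The documents do not state this, so the point is conditional on it.

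If it is so, neither reading of distance measures the shift well:

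- **Unsigned.** This is the more literal reading, though the text does not settle it. A subject whose baseline leans against the shift moves toward or across vertical and scores a small rise or even a fall. The mean change shrinks and its spread grows.
- **Signed in room coordinates.** Right-ear and left-ear shifts have opposite signs and offset each other in the pooled mean.

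What is at stake is mainly the second objective: with five subjects per experiment, a real after-effect could be missed or reported as smaller than it is. Leaving the rule open also allows a choice, after the data are seen, between scorings that can give very different answers.

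**Working it through.** The plan states no power, SD or expected effect, so there is no figure to reproduce.

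**Inputs from the documents.** n = 5 per experiment, five trials per assessment, paired t-test, alpha 0.05, ear randomised.

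**Assumptions.** Two-sided test; independent 1:1 ear allocation; one pre and one post set of trials (the tested pair is not specified); trial SD 1 degree; baseline tilt centred on 0 with SD 0.5 to 2; shift 1 to 3 degrees; occasion-to-occasion SD 0 or 0.5; between-subject SD of the shift 0, 0.5 or 1.

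**Step 1: signed, room coordinates.** With R right-ear and L left-ear subjects, the share of the mean shift kept is (R − L)/5 in absolute value.

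| Split | Probability | Share kept |
|---|---|---|
| 3:2 | 20/32 = 62.5% | 1/5 = 20% |
| 4:1 | 10/32 = 31.25% | 3/5 = 60% |
| 5:0 | 2/32 = 6.25% (1 in 16) | 100% |

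The average share kept is 0.625 × 0.2 + 0.3125 × 0.6 + 0.0625 × 1 = 0.375.

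**Step 2: unsigned distance.** For baseline x and shift d, the change | |x + d| − |x| | cannot exceed |d|. With d = 1.5, a subject starting at +1 goes from distance 1 to 2.5, a rise of 1.5. A subject starting at −1 ends at +0.5, so distance falls from 1 to 0.5. Both moved 1.5 degrees, yet their mean recorded change is (1.5 − 0.5)/2 = 0.5.

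For a normal value with mean μ and SD σ, the expected distance is σ√(2/π)·exp(−μ²/2σ²) + μ[1 − 2Φ(−μ/σ)], where σ² is the sum of the baseline, occasion and trial variances. With the same shift in every subject:

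- Baseline SD 1, shift 1.5, no occasion noise (σ² = 2): (1.710 − 1.128)/1.5 = 38.8% of the shift recovered.
- Same with occasion SD 0.5 (σ² = 2.25): (1.750 − 1.197)/1.5 = 36.9%.
- Baseline SD 0.5, shift 3 (σ² = 1.25, or 1.5 with occasion noise): 70% and 68%.

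**Step 3: power.** For the ear-aligned value, the SD of a subject's change is √(2 × occasion² + 2 × trial²/5 + shift SD²), and power follows from the noncentral t with 4 degrees of freedom. Unsigned power (mean of the unsigned trials) is simulated. Baseline SD 1, mean shift 1.5:

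| Occasion SD | Shift SD | SD of aligned change | Power, aligned | Power, unsigned |
|---|---|---|---|---|
| 0.5 | 0.5 | √1.15 = 1.07 | 0.65 | 0.15 |
| 0.5 | 1 | √1.90 = 1.38 | 0.46 | 0.14 |
| 0.5 | 0 | √0.90 = 0.95 | 0.75 | 0.16 |
| 0 | 0 | √0.40 = 0.63 | 0.97 | 0.23 |

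Room-coordinate scoring gives about 0.06 to 0.07 in these cells. At the mild end (baseline SD 0.5, shift 3, same shift in all), unsigned power is 0.94 with occasion noise and 0.99 without, against 1.00 aligned. Averaging all five sessions on each side does not cure the problem: with an identical shift, baseline SD 1 and shift 1.5, power is 0.27 to 0.30 unsigned against 1.00 aligned.

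**Step 4: no shift.** Simulated rejection is 4.4% to 5.1% under every scoring.

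**Step 5: choice of parameter (illustrative).** The documents give no selection rule. Assume the larger mean change wins, the ear is the same in A and B, and the true shifts are 1.0 and 1.5. The weaker option is then picked 12%, 17% and 28% of the time unsigned at baseline SD 0.5, 1 and 2, against 11% aligned. With occasion SD 0.5 the figures are 20%, 25% and 34%, against 20%.

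**The case against.** **The premise is inferred.** The outcome section says only that SVV is influenced by otolith function. It does not say that static SVV, measured upright, shifts to one side or reverses with the ear. This stands: without lateralisation the point does not arise.

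**Unsigned error may be intended.** The outcome is framed as accuracy in setting a line to vertical, and for that construct distance is coherent. If training raises error in no consistent direction, the aligned value would miss it. This also stands, and is why unsigned distance should be kept as secondary. It does not remove the gap: the plan does not say which version is meant.

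**The sizes depend on assumptions.** This stands too. A reader might take 0.23 against 0.97 as this trial's loss. The documents do not support that, because it assumes no occasion noise and an identical shift in all five subjects. With shift SD 1 and occasion SD 1, power is 0.09 against 0.29, so n = 5 fails either way.

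**Stronger readings that fail.** A reader might infer that false positives are inflated; the rejection rate with no shift is about 5%. A reader might infer that signed values always cancel; a 5:0 split loses nothing. A reader might infer that the wrong distance, duration or schedule will be chosen; at baseline SD 0.5 the scoring makes almost no difference, and the selection rule is itself assumed.

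**Conclusion.** The concern holds conditionally and should be fixed; confidence is medium. The ear is randomised, the outcome has neither sign nor ear reference, and the ears are pooled. Nothing in the supplied text resolves this. If the after-effect is lateralised, unsigned scoring attenuates it, and room-coordinate scoring partly cancels it in 15 of 16 allocations.

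In the illustrative middle case with realistic heterogeneity, alignment raises power from roughly 0.15 to between 0.46 and 0.65. When the shift is large relative to baseline tilt, little power is lost, but the estimate is still understated: about 68% to 70% of the shift is recovered. The consequence is a missed or understated effect under the second objective. Any effect on parameter choice is secondary, and small when baseline spread is small. Alignment does not make five subjects adequate for small or highly variable shifts.

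**What to change.** Add to the outcome definition and the Statistical Analysis Plan:

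*Each SVV trial is recorded as a signed angle, positive when the top of the line is tilted toward the subject's right. The five signed trials are averaged. The average is multiplied by +1 if the right ear was off-axis and by −1 if the left ear was, so that positive means tilt toward the trained ear. The two-sided paired t-tests use the pre-to-post change in this ear-aligned value. Unsigned distance is reported as a secondary outcome.*

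State also whether a subject keeps the same ear across conditions A and B.

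**Cost.** One sentence in the outcome definition and one recoding rule, with no new measurement and no change to training. The downside is that the aligned value would miss a purely non-directional rise in error, which the secondary analysis is there to catch.

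**Dependency.** The rule needs the sign of each trial. Ethics approval dates from December 2015 and the document from September 2021, so data may already exist. If only unsigned distances were kept, they cannot be recoded; the report should then say so and present the unsigned change with this limitation.

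### The SAP sets out to examine how distance, duration and schedule affect SVV, but the only test it names is pre- to post-centrifugation change; no A-versus-B contrast is written

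*Combined protocol and SAP*

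**What the plan says.** Study Objectives gives two goals. The first is "to determine optimal stimulus parameters (off-axis distance of the rotary chair, duration of off-axis rotation, and training schedule", with the chosen values intended for later use in patients with otolith dysfunction. The second is "to demonstrate otolith plasticity with a given set of stimulus parameters".

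The Statistical Analysis Plan opens its inferential sentence with "To examine the extent to which centrifugation parameters (distance, duration, schedule) impact the primary outcome" and then names the method: "paired t-tests will be used to examine change in static SVV (pre- to post-centrifugation". Beyond that it gives descriptive summaries, an alpha of 0.05 and no multiplicity adjustment.

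The experiments compare two levels each, with 5 subjects per experiment:
- **Experiment 1:** 3.5 cm (A) and 7.0 cm (B). It has "training at chair position (A) followed by (B) with at least 2 weeks in between each training session until static SVV returns to normal".
- **Experiment 2:** 1 minute (A) and 3 minutes (B) of off-axis rotation, A first, at least 2 weeks apart.
- **Experiment 3:** consecutive (A) and intermittent (B) schedules. The text has subjects complete schedule B after Experiment 2.

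The outcome is recorded as "Static SVV (5 trials) at start/end of each session", and "the software calculates the distance (in degrees) from vertical". The side of training is "randomized for right or left ear off-axis".

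**The concern.** The question in the first half of the SAP sentence is comparative: does 7.0 cm do more than 3.5 cm, 3 minutes more than 1, one schedule more than the other? The comparison in the second half is before versus after. A pre-post test within a condition can show that SVV moved under that condition. It does not show whether the two conditions moved it by different amounts.

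The choices cascade. Experiment 1 fixes the distance for Experiments 2 and 3, Experiment 2 fixes the duration for Experiment 3, and the resulting set is meant for patients. Choosing descriptively is legitimate with 5 subjects. But the plan attaches a test at alpha 0.05 to the parameter question, and as worded that test says nothing about how uncertain the A-B difference is. No rule for calling a level optimal is written either.

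**Working it through.** **Step 1. Match each objective to a quantity.** Let c_A and c_B be one subject's SVV change (post minus pre) under A and B.
- Objective 2 asks whether mean c_A, or mean c_B, differs from zero. The named pre-post paired t-test does this.
- Objective 1 asks about the mean of c_B − c_A. A pre-post test of A uses only c_A and a pre-post test of B uses only c_B, so neither estimates this difference or its standard error. The descriptive summaries would allow condition means to be ranked, but no interval is planned for their difference.

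**Step 2. Precision of the missing contrast.** The documents give no SD, effect size or correlation, so results are in SD units and effects are assumed. n = 5 and alpha = 0.05 come from the protocol and SAP. Two-sided testing is assumed, since sidedness is not stated. With df = 4, the critical t is 2.776.
- 95% CI half-width = 2.776 / √5 = 1.24 SD of the paired differences.
- Power of the paired t-test (noncentral t, noncentrality d√5): 0.141 at d = 0.5, 0.401 at d = 1.0, 0.711 at d = 1.5. 80% power needs d = 1.68.

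**Step 3. Reliability of ranking by means.** With true difference d in SD of the paired differences, the chance that the lesser condition has the larger mean is Φ(−d√5):
- d = 0.25: Φ(−0.559) = 0.288
- d = 0.5: Φ(−1.118) = 0.132
- d = 1.0: Φ(−2.236) = 0.013

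Writing the contrast does not alter this ranking. It reports how uncertain the ranking is.

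**Step 4. What the fixed order does to the contrast.** A comes before B for every subject, so mean c_B − c_A estimates condition plus period. Suppose the conditions are equal and period alone adds 0.5 SD of change to B. With correlation r between c_A and c_B, the SD of the paired difference is √(2(1 − r)) SD of change. The standardized shift is therefore 0.5/√(2(1 − r)) = 0.35, 0.50 and 0.79 at r = 0, 0.5 and 0.8. The test then rejects in 10%, 14% and 28% of experiments, nearly all in favour of B. With a period shift of 0.25 SD the figures are 6%, 7% and 11%.

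**Step 5. Experiment 3.** If schedule A is the Experiment 2 arm selected for its larger mean, that mean is biased upward even when all conditions are equal. The expected excess is √(2(1 − r)/5) / √(2π) SD of change:
- r = 0: 0.632 / 2.507 = 0.25
- r = 0.5: 0.447 / 2.507 = 0.18
- r = 0.8: 0.283 / 2.507 = 0.11

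**Step 6. The change score.** Start and end readings in 5 sessions give 2 × 5 = 10 readings per condition. The plan does not say which readings, or which combination, form the pre-post pair. Nor does it say whether the sign of the deviation is kept. If signed values were averaged over right-ear and left-ear training without re-orientation, opposite shifts could cancel.

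**The case against.** The best defence is that a paired comparison of change scores between A and B was meant: the lead-in names the parameters, the design is within-subject and the method is paired. That cannot be excluded. But the parenthesis in the SAP defines the comparison as pre to post, and no wording pairs A with B. If the contrast was intended, one sentence settles it.

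A second defence is that this is a five-subject parameter-finding study in healthy controls, where a descriptive choice is reasonable and a formal contrast will usually be inconclusive. This stands, and it limits the weight of the point. No parameter choice, subject or visit would change.

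A third is that a within-session, start-to-end change is a natural reading of the measurement schedule, so the outcome is not wholly undefined. This also stands in part. What is missing is which sessions count or how they are combined, together with the sign convention. These are secondary details.

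Two stronger readings are tempting. A reader might infer that the plan would pick the condition whose pre-post test is significant when the other is not, and so would often separate equal conditions falsely. The documents contain no such rule, and their descriptive summaries allow ranking by means, so an error rate computed under that rule does not measure this plan. A reader might also infer that a B-minus-A interval excluding zero would establish the better condition. The fixed order rules that out: the return-to-normal criterion in Experiment 1 can reduce carryover but does not remove period effects, and the Experiment 2 text does not state that criterion.

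**Conclusion.** The point holds in limited form. Followed as written, the SAP tests objective 2 and supplies no interval for the A-B difference behind objective 1, although its own sentence is aimed at that question. A better analysis of the readings already scheduled is available.

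Its size is modest: the correction changes what can be claimed about the chosen parameters, not which condition ranks higher. It belongs at the low end of what should be fixed. Confidence is high that the contrast is not written; whether it was intended is unknown. The 1.24 SD half-width follows from n = 5 and a two-sided 95% interval. The power, ranking, period-shift and selection-bias figures rest on normality and on assumed effects and correlations. The documents do not support saying that an A-B comparison is impossible or was never made.

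**What to change.** Amend the Statistical Analysis Plan as follows.

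- **Objective 1, Experiments 1 and 2.** Compute each subject's SVV change under A and under B from one prespecified definition: which session readings are used, and the sign relative to the off-axis ear if sign is stored. If only unsigned distance is stored, say so and use it. Report the mean of B minus A with its 95% CI (paired t, n = 5, df = 4).
- **Selection and claims.** The larger mean change may decide what goes forward. Report the contrast as the difference seen in this fixed sequence, condition plus period, with no superiority claim from the CI alone.
- **Objective 1, Experiment 3.** State that schedule A is the selected Experiment 2 arm, as the text suggests, and report the comparison as descriptive because that arm was picked for its larger mean.
- **Objective 2.** Keep the pre-post paired t-tests per condition.

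The document is dated September 2021. If outcome data have already been examined, label the contrast post hoc.

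The cost is SAP wording, with no new subjects or visits. Re-orienting by ear is possible only if sign has been stored, which the documents do not say. The downside is a wide interval that will usually include zero while the higher-ranked condition still goes forward. The confounding of order with condition remains.

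### The pre- to post-rotation t-tests cannot by themselves support the claim of otolith plasticity, because no condition separates the off-axis stimulus from the rest of the session

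*Combined protocol and SAP*

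**What the plan says.** Study Objectives sets two aims in healthy controls: to find the best stimulus parameters, and "to demonstrate otolith plasticity with a given set of stimulus parameters". The parameters are meant to be carried forward to patients with otolith dysfunction.

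The Statistical Analysis Plan names one inferential method: "paired t-tests will be used to examine change in static SVV (pre- to post-centrifugation". It adds "Alpha level is 0.05" and "No adjustments will be made for multiple comparisons".

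All training is off-axis. Experiment 1 compares 3.5 with 7.0 cm, Experiment 2 compares 1 with 3 minutes of off-axis rotation (OAR), and Experiment 3 compares a daily with a twice-weekly schedule. No on-axis-only (0 cm), sham or no-rotation condition is listed. The cycle in Experiment 1 is "90 sec accelerate to/ maintain constant velocity on-axis rotation; 1 min OAR at constant velocity; 60 sec to decelerate", and SVV is read only before and after a whole session of five cycles.

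The order of conditions is fixed: "Each subject will complete training at chair position (A) followed by (B"). Study Protocol randomises the ear placed off-axis and has the direction of rotation "standardized so that subjects are facing forward in the direction of rotation". The outcome section says that otolith function influences SVV. It does not say that SVV is specific to it.

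**The concern.** Objective 2 makes a claim about one organ and one cause. The planned test asks only whether SVV differs after a session from before it. Between the two readings the subject has been accelerated, spun on-axis, moved off-axis, decelerated and tested again. A shift produced by any of these would count equally towards significance, and the planned analysis could not tell them apart. It could then be reported as otolith plasticity and used to justify training patients.

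**Working it through.** The plan gives no power calculation, expected effect or SD, so it has no figure of its own to reproduce.

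**Inputs.** Five subjects ("Determination of optimal distance of OAR (n = 5 subjects")); alpha 0.05, with sidedness not stated and taken as two-sided; acceleration 5 deg/s² and velocity 300, whose column is headed deg/s² and is read here as deg/s; timings from the experiment tables.

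**1. What a cycle contains**
- Spin-up: 300/5 = 60 s, leaving 90 − 60 = 30 s of steady on-axis rotation.
- Cycle length: 90 + 60 + 60 = 210 s with 1 min OAR; 90 + 180 + 60 = 330 s with 3 min.
- Explicitly on-axis: 90/210 = 43% and 90/330 = 27%.
- If the 60 s deceleration is also on-axis, which the text does not say: 150/210 = 71% and 150/330 = 45%.

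These are shares of time, not of effect.

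**2. The planned test when there is no otolith effect**

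Let the change (post minus pre) have mean m, all from non-otolith sources, and between-subject SD s. The paired t statistic is then noncentral t with 4 df and noncentrality (m/s)√5. The critical value is 2.776.

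| m/s (assumed) | noncentrality | chance of significance |
|---|---|---|
| 0 | 0 | 5% |
| 0.25 | 0.56 | 7% |
| 0.5 | 1.12 | 14% |
| 1.0 | 2.24 | 40% |
| 1.5 | 3.35 | 71% |
| 2.0 | 4.47 | 91% |

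**3. What a 7.0 versus 3.5 cm contrast can add**

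In Experiment 1 both conditions have the same angular profile and the same session length (5 × 210 s = 17.5 min). Only the linear stimulus differs. With ω = 300 × π/180 = 5.24 rad/s, ω²r at the chair offset is 0.96 m/s² (0.098 g) at 3.5 cm and 1.92 m/s² (0.196 g) at 7.0 cm. A non-otolith shift common to both conditions therefore cancels in the difference of changes. There are two limits:
- *Order.* 3.5 cm always comes first. A first-to-second-block difference of 0.5 or 1.0 SD of the difference score would by itself give significance 14% or 40% of the time, by the table above.
- *Power.* With n = 5, 80% power needs 1.68 SD of the difference score. In SDs of a single change score this is 1.68 × √(2(1 − ρ)): 2.38, 2.06, 1.68 or 1.19 for an assumed correlation ρ of 0, 0.25, 0.5 or 0.75.

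Experiment 2 does not offer the same check, because the longer OAR also lengthens the session (5 × 330 s = 27.5 min against 17.5 min).

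**4. What alignment to the trained ear can add**

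Suppose the ear is drawn once per subject. A shift m that does not depend on side then enters the ear-aligned change as +m for one ear and −m for the other. It averages to zero over the randomisation, but not exactly in five subjects: the best split, 3:2, leaves (3m − 2m)/5 = m/5. A directional after-effect of rotation would not cancel if rotation direction follows the ear. The facing-forward rule suggests that it does, but the text does not say so.

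**The case against.** Much of the case on the other side is sound.

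- **No non-otolith shift is documented.** The 14% to 91% range describes what would follow from an assumed shift; it is not an estimate. Scientific Background also says that adaptation after centrifugation has already been shown. This stands. A reader might infer that any SVV change in this trial is an artefact of rotation or retesting, and the documents do not support that.
- **Most of the cycle need not be non-otolith.** A reader might take 71% as established. It requires the chair to be back on-axis before it slows, and only the first 90 s is labelled on-axis.
- **The choice of distance is less exposed.** A shift common to both offsets favours neither, order aside. A reader might infer that the parameter selection fails for the same reason as objective 2; that does not follow.
- **Ear randomisation helps.** It deals on average with effects that do not depend on side, such as retesting, so it would be wrong to dismiss it. But the SAP plans no such analysis and does not say whether SVV is recorded with its sign.
- **Start-of-session readings from the second session on** come a day or more after the last rotation and bear on persistence. The SAP does not assign them that use, and they still carry retesting effects.
- **One on-axis session is not a clean remedy.** A reader might infer that a single such session, given first, would restore the 5% error rate whatever the shift. In simulation the rate does return to about 5% (0.049 to 0.050), but only if the shift is equal in both conditions and nothing carries over. A lone first session set against a five-session block confounds condition with order and exposure.

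None of this makes the pre-post test specific to the otoliths.

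**Conclusion.** The point holds in a limited form: significance in the planned tests, taken alone, does not establish otolith plasticity. That follows from the design and does not depend on the size of any non-otolith shift. The error rates do: 14% to 91% for shifts of 0.5 to 2 SD, assuming normally distributed changes, five subjects and a two-sided test.

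It would go too far to say that the trial can provide no evidence of plasticity. Experiment 1 and the ear randomisation both carry relevant information, which the SAP does not use. The absence of a control is judged on Study Protocol, the experiment tables and the SAP, where such a condition would be expected to appear.

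**What to change.** Amend the SAP, using measurements that the plan already takes:

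- **(a) Wording.** State that pre-post significance alone will be reported as SVV change after a rotation session, not as otolith plasticity.
- **(b) Distance contrast.** In Experiment 1, add a paired t-test of (SVV change at 7.0 cm minus SVV change at 3.5 cm), with change defined identically for both blocks. Treat a larger change at 7.0 cm as supporting evidence only, because the order is fixed. State that finding no difference would not exclude an otolith effect.
- **(c) Ear-aligned analysis.** Analyse signed SVV change aligned to the trained ear, if the sign is retained. State that this removes side-independent effects on average, but not a directional after-effect if rotation direction is tied to the ear.

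If outcome data have already been examined, label (b) and (c) as post hoc.

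**Cost.** SAP text and two further analyses, which add to a set of tests not adjusted for multiplicity. Objective 2 gets a more limited conclusion, and power at n = 5 is low, so a null contrast would say little.

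**Optional.** A 0 cm control with the same rotation profile would be the stronger design. To be fair it needs a matched session count and balanced order: 5 subjects × 5 sessions = 25 extra sessions. That is 20% of the 125 planned (50 + 50 + 25) if the same five subjects do every block. It is not part of the low-cost fix.
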